18.9.2 Time to first flare, flare-free status, AFR

KM estimates for the time to first flare: proc LIFESTEST with SAS

The KM estimates and KM curve will be presented using the LIFESTEST procedure as follows:

```
ODS listing gpath="<gpath>";  
ods graphics on;  
proc lifetest data=<dataset> outsurv=<OutDataset> plots=(survival(atrisk=0 to  
&LastPatientAtRisk. by <step>)) method=km;  
time aval*cnsr(1);  
strata TreatmentGroup;  
run;  
ods graphics off;
```

In order to get the KM percentiles and their corresponding 95% CI, the following steps will be performed:

1. Run PROC LIFESTEST ‘standard’: need outsurv and ProductLimitEstimates
2. From ProductLimitEstimates, create one dataset per group, keeping only events and non-missing survival estimates
3. In each group dataset, compute LOGLOG estimate of each survival estimate: formula
$$\frac{g(S(t)) - g(1 - 0.25)}{g'(S(t))\sigma(S(t))}$$
from SAS support (1): where S is survival, sigma is stderr, g=LOG(-LOG(..)) and g' is first derivative of the function. Replace 0.25 with expected percentile – 0.05, 0.10, 0.15, 0.20 - (example in SAS is for first quartile)
4. Then compute 95% CI: lowest/highest values from (1) that lie between $\pm z_{1 - \frac{0.05}{2}} = \pm 1.965$
5. Retrieve the p percentile value from outsurv
6. Combine with the datasets containing CI

In addition to the KM estimates, the subgroup analysis can be implemented using the following code:

```
proc lifetest data=<dataset> outsurv=<OutDataset>;  
time AVAL*CNSR(1);  
strata &TRT.N;  
where SLEDAI_2K_screening = <value_of_interest>;  
run;
```

Log-rank p-value:

```
proc lifetest data=<dataset> notable;  
time aval*cnsr(1);  
strata Region Race SLEDAI_2K_screening / group= TreatmentGroup test=logrank  
diff=control('1');  
ods output SurvDiff=SurvDiff;  
run;
```

For primary analysis of key secondary endpoint *Time to first severe (BILAG A) flare* output the 1-sided p-value ($\alpha=0.025$) as below:

- When the HR favors the active treatment (i.e. $HR \leq 1$), one-sided p-value = two-sided p-value / 2
- When the HR does not favor the active treatment (i.e. $HR > 1$), one-sided p-value = 1 – (two-sided p-value / 2).

Cox model for the time to first flare: proc PHREG with SAS

The Cox regression model will be performed using the PHREG procedure from SAS – get HR and 95%CI:

```
proc phreg data=<dataset>;
  class TreatmentGroup(ref='Placebo') Region Race SLEDAI_2K_screening;
  model AVAL*CNSR(1) = TreatmentGroup Region Race
                    SLEDAI_2K_screening / RL TIES=DISCRETE;
  Hazardratio TreatmentGroup / DIFF=REF;
run;
```

In addition to the Cox regression model, the subgroup analysis can be implemented using the following code:

```
proc phreg data=<dataset>;
  class TreatmentGroup(ref='Placebo') SLEDAI_2K_screening;
  model AVAL*CNSR(1) = TreatmentGroup SLEDAI_2K_screening
                    TreatmentGroup*SLEDAI_2K_screening / TIES=DISCRETE;
  Hazardratio TreatmentGroup / DIFF=REF;
run;
```

For trend test for key secondary endpoint time to first severe (BILAG A) flare:

```
proc phreg data=<dataset>;
  class TreatmentGroup Region Race SLEDAI_2K_screening / param=GLM;
  model AVAL*CNSR(1) = TreatmentGroup Region Race
                    SLEDAI_2K_screening / TIES=DISCRETE;
  ESTIMATE "Trend linear in treatment" TreatmentGroup -3 -1 1 3;
  CONTRAST "Trend linear in treatment" TreatmentGroup -3 -1 1 3 / e;
run;
```

Sensitivity analysis of first severe BILAG A flare:

```
/******
  STEP 1 : creation of monotone missing data structure
******/

/** _burn-in_NBITER_ will have to be adjusted by a convergence plot,
if convergence is not yet diagnosed after 200 iterations ***/
title "Step 1 : Create monotone structure" ;
proc MI data=<Dataset> out=outMAR1 seed=&seed. nimpute=&nimpute. noprint;
  var
  TreatmentGroup
  black (0=non-black 1=black)
  SLEDAI_2K_screening
  US (0=not US 1=US region)
```

```
West (0=not Western Europe, 1=Western Europe region)
Jap (0=not Japan region, (1=Japan region)

Resp_base Resp_Day14-Resp_Day52;

/* continue to the last endpoint */

;
mcmc chain=single initial=EM nbITER=200 NITER=100 impute=monotone ;
EM MAXITER = 5000 ;
run ;

/*****
STEP 2 : Apply multiple imputation
*****/
title "Step 2 : Apply MI procedure (MAR pattern)" ;
proc mi data=outMAR1 nimpute=1 seed=&seed. out=outMAR2 noprint;
  by _Imputation_;
  class TreatmentGroup race region SLEDAI_2K_screening
    Resp_base Resp_Day14-Resp_Day52;
  var TreatmentGroup race region SLEDAI_2K_screening
    Resp_base Resp_Day14-Resp_Day52;
  monotone logistic;
run;

/*****
STEP 3 : Create dataset with Time to
*****/
This should be define in specification of ADAM and same rule should be applied to
outMAR2 dataset by imputation.

/*****
STEP 4 : Create estimate on imputed dataset
*****/
proc phreg data=<dataset>;
  by _Imputation_;
  class TreatmentGroup(ref='Placebo') Region Race SLEDAI_2K_screening;
  model AVAL*CNSR(1) = TreatmentGroup Region Race
    SLEDAI_2K_screening / RL TIES=DISCRETE;
  ods output ParameterEstimates=_es; run;

run;

/*****
STEP 5 : Combined estimates
*****/
/* Combine model coefficients. */
proc sort data=_es;
  by Parameter ClassVal0 _Imputation_;
  run;
proc mianalyze data=_es;
  by Parameter ClassVal0;
  modeleffects Estimate;
  stderr stderr;
  ods output ParameterEstimates = _es_mianal;
run;

/*Exponentiate in order to obtain hazard ratio estimates and confidence intervals */
data resprefix_hr;
  set _es_mianal;
  Log_HR_Comb=Estimate;
```

```
HR_comb=exp(Estimate);  
HR_LCL_comb=exp(LCLMean);  
HR_UCL_comb=exp(UCLMean);  
keep Parameter ClassVal0 Log_HR_comb HR_comb HR_LCL_comb HR_UCL_comb Probt;  
rename Probt=HR_pval_comb;  
run;
```

Logistic regression for the flare-free status

The same procedure as in Appendix 18.9.1 must be applied.

NB model for BILAG A Severe flare / BILAG A or 2B Moderate to Severe flare/ SFI Severe flare

The NB model will be performed using the GENMOD procedure from SAS:

```
proc genmod data=<Dataset>;  
  class TreatmentGroup Region Race SLEDAI_2K_screening;  
  model AVAL = TreatmentGroup Region Race SLEDAI_2K_screening/ alpha=0.05  
  offset=LOGTIME  
  DIST=NB MAXITER=<MaxIter>;  
  ESTIMATE "log flare RR evobrutinib 25mg QD vs placebo" TreatmentGroup -1 1 0 0  
  / EXP;  
  ESTIMATE "log flare RR evobrutinib 75mg QD vs placebo" TreatmentGroup -1 0 1 0  
  / EXP;  
  ESTIMATE "log flare RR evobrutinib 50mg BID vs placebo" TreatmentGroup -1 0 0 1  
  / EXP;  
  ods output estimates=estimates1;  
run;
```

where <maxIter> is the number of iteration (must be sufficiently high to run the model). The offset is equal to the logarithm of years on treatment.

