8.2.2 Analysis Sets

Table 3 provides the definitions of the Analysis Sets and their purposes.

[figure not shown]
The analysis sets for PA will be drawn from all subjects randomized as of November 28, 2018 (n = 469), see Sections 6.2 and 7. Subjects not randomized (screen failure) will be included in PA analysis set if their screening date is on or before November 28, 2018. For the LTE analysis, the analysis sets will be drawn from all subjects who enter the LTE.

For analysis on HDA subpopulation, all subjects with SLEDAI-2K ≥ 10 at Screening will be included. The corresponding analysis sets will be drawn as specified above depending on the analysis (PA, LTE analysis).

Table 3: Analysis Sets

Analysis Set	Definition	Purpose
Enrolled	The Enrolled analysis set will include all subjects who sign the informed consent form.	The purpose of this analysis set is to count how many subjects signed the informed consent

ITT (Intent-To-Treat) Analysis Set	The ITT analysis set will include all randomized subjects. Subjects will be analyzed according to randomization treatment.	The ITT will be used for demographic/baseline characteristics.
mITT (modified Intent-To-Treat) Analysis Set	The mITT analysis set will include all randomized subjects who have received at least one dose of IMP (evobrutinib or placebo) and have at least one Baseline and one post-Baseline disease assessment (among the following: SFI, SLEDAI-2K, PGA, BILAG 2004, CLASI). Subjects will be analyzed according to randomized treatment. Subjects with Protocol Deviation (PD) code equal to PDEV80 are excluded from mITT.	The mITT will be used for all efficacy endpoints. The mITT will be used for demographic/baseline characteristics in case more than 10% of ITT are excluded from mITT.
Safety Analysis Set (SAF)	The Safety analysis set will include all subjects who have received at least one dose of IMP (evobrutinib or placebo). Subjects will be analyzed according to the actual treatment they receive.	The SAF will be used for the analysis of medications, exposure/compliance and safety endpoints.

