14.2.1 Definitions

SRI-4 response among serologically active subjects

The SRI-4 response will be analyzed at Week 52 among subjects who are serologically active at screening, i.e., positive anti-dsDNA or low complement levels.

Time to first severe (BILAG A) flare

A severe (BILAG A) flare is defined as at least one BILAG A score in any organ system due to items that are new or worse, compared to the BILAG evaluation at the previous visit, during the 52-week treatment period. “Due to items that were new or worse” means that if the assigned Grade A/B or C contains ANY ITEM which is WORSE or NEW, such grade will be included into the flare consideration. This is valid for clinical organ domains. For laboratory organ domains (i.e. renal and hematological) where items are not worse/new, there has to be an increase in score from B to A or C to B for flare to be considered. Appendix 18.1.1 provides further details on BILAG evaluation. EAC will review the dry-run BILAG analysis dataset to ensure appropriateness and correctness of programmed BILAG flare derivation. Further details can be found in the EAC Charter.

Since subjects are only to be assessed for BILAG flare at discrete planned visits, the corresponding date of visit will be used to derive the time to first severe (BILAG A) flare as follows:

$$\begin{aligned} & \textit{Time to first severe BILAG A flare (days)} \\ &= \textit{Date of visit where the first severe BILAG A flare has been diagnosed} \\ & - \textit{Date of randomization} + 1 \end{aligned}$$

The following censoring rules will be used:

- A subject discontinuing the 52-week treatment period prior to Week 52 without severe flare will have his/her time to first severe flare right-censored at the last time point at which flare could be assessed (i.e. treatment discontinuation date).
- A subject completing the 52-week treatment period without severe flare will have his/her time to first severe flare right-censored at Week 52.

Additionally, a sensitivity analysis will be performed based on Multiple imputation approach of severe flare at each visit up to week 52:

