14.2.2.2 Analysis of Time to first severe BILAG A flare

The time to first severe flare will be analyzed on the mITT Analysis Set using a stratified log rank test with treatment as main effect and stratification variables used in the randomization (race, screening SLEDAI-2K total score and region) as covariates. The one-sided p-values ($\alpha=0.025$) from the stratified log rank test for treatment comparisons vs placebo will be reported. The multiplicity adjustment procedure as outlined in Section 14.1.2.4 will be applied to assess statistical significance.

In addition, a Cox proportional hazards regression model including treatment as factor and the stratification factor at randomization as covariates will be performed. Ties will be handled by replacing the proportional hazards model by the discrete logistic model. The HR together with its 95% CI will be presented as determined by the proportional hazards model. Placebo group will be used as reference group. The assumptions of proportional hazards will be verified graphically (the curves representing the relative risk will be plotted for each treatment group and should be parallel).

KM estimates (product-limit estimates) will be presented by treatment arm together with a summary of associated statistics (median, Q1 and Q3, minimum and maximum) including the corresponding two-sided 95% CI of the median. The KM 5%, 10%, 15% and 20% percentiles as well as the corresponding 95% CI will also be presented. In addition, the number of severe flares by treatment group will be presented.

The KM curves will also be provided for each treatment group.

As sensitivity analyses, stratified log-rank test, Cox model, KM estimates and KM curves will be repeated:

- Using MI as stated in Section 14.2.1,
- On PP analysis set if the size of these analysis sets differs substantially (>10%) from mITT.

In addition, a test for trend in dose-response, using the same Cox model, will be reported as a supportive analysis, using contrast statement and (-3 -1 1 3) coefficients.

An example of SAS code is available in Appendix 18.9.

If there is model convergence problem due to for example zero cells in covariates, appropriate method will be applied to resolve the issue.

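### The programmed 95% CIs for the Kaplan-Meier flare percentiles stop at the last flare time inside the band, so the upper limit is almost always one flare time too early and is finite when it is not estimable

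*SAP*

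**What the plan says.** SAP 14.2.2.2 states: "The KM 5%, 10%, 15% and 20% percentiles as well as the corresponding 95% CI will also be presented". Appendix 18.9.2 then gives the steps for computing them:

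- Step 2: "create one dataset per group, keeping only events and non-missing survival estimates". Censored rows are dropped.
- Step 3: on each remaining row, compute (g(S(t)) − g(1−p)) / (g′(S(t))·σ(S(t))), "where S is survival, sigma is stderr, g=LOG(-LOG" and g′ its first derivative, for p = 0.05, 0.10, 0.15 and 0.20.
- Step 4: "Then compute 95% CI: lowest/highest values from (1) that lie between" ±z at 1 − 0.05/2, printed as ±1.965.
- Step 5: take the point percentile separately, from the survival output dataset.

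No step moves the upper limit past the last accepted flare row, and no step says when an upper limit is not estimable.

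Two features of the endpoint in 14.2.1 matter here. BILAG flares are dated by visit ("Since subjects are only to be assessed for BILAG flare at discrete planned visits"), and Table 51 places those visits 28 days apart. Flare-free completers are "right-censored at Week 52".

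**The concern.** The step 3 inequality defines a set of times, and the interval is that set. Between two flare times S(t) and its standard error do not change. Every time after the last accepted flare therefore still satisfies the inequality until a flare pushes the statistic out on the low-survival side. The upper limit should be that next flare time. If no such flare occurs before follow-up ends, the set is open and the limit is not estimable.

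Keeping only flare rows and taking the highest one inside the band gives a different answer. It stops one flare time early, and where the set is open it returns the last accepted flare day as though it were a limit.

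At stake is how each arm's flare timing reads in the report. An interval can end at its own point estimate, or a percentile shown as not reached can carry a finite upper limit inside the year.

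**Working it through.** **Inputs.** The rule and statistic are from 18.9.2 and the percentiles from 14.2.2.2. Arm size is 469/4, about 117, from 8.2.2 ("The analysis sets for PA will be drawn from all subjects randomized as of November 28, 2018 (n = 469"). The documents give no flare incidence and no drop-out rate for this endpoint, so the data below are assumed. With no losses, Greenwood's formula reduces to SE = √(S(1−S)/n). For g = log(−log S), g′(S) = 1/(S·ln S), so the statistic is positive while S exceeds 1−p and negative once S is below it.

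**Example 1 (assumed): n = 117, one first flare at each visit from Day 29 to Day 365, two on Day 57 (14 in all), none lost.**

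5th percentile, g(0.95) = −2.970:

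- Day 253, 10 flares so far: S = 107/117 = 0.9145, g = −2.415, g′·SE = −12.23 × 0.02585 = −0.316. Statistic = 0.555/(−0.316) = −1.75, inside.
- Day 281, 11 flares: S = 106/117 = 0.9060, g = −2.316, g′·SE = −11.18 × 0.02698 = −0.302. Statistic = 0.655/(−0.302) = −2.17, outside.

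The SAP returns Day 253. The set runs to Day 281.

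For the higher percentiles, the last flare (Day 365) leaves S = 103/117 = 0.8803. The statistic there is −0.71 for the 10th percentile and +0.91 for the 15th. Both are inside the band, so both sets are open. For the 20th it is +2.09, and no flare time falls in the band.

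| Percentile | Point estimate | SAP rule | Full set |
|---|---|---|---|
| 5th | Day 141 | 29 to 253 | 29 to 281 |
| 10th | Day 309 | 141 to 365 | 141 to not estimable |
| 15th | not reached | 253 to 365 | 253 to not estimable |
| 20th | not reached | nothing returned | not estimable |

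**Example 2 (assumed): n = 100; flares 4, 3, 3, 3, 2, 2, 2, 1, 1 on Days 29, 57, 85, 113, 141, 169, 197, 253, 309; 79 censored at Day 365.** For the 5th percentile the statistics on Days 29, 57 and 85 are 0.46, −0.92 and −2.28. The SAP interval is (29, 57), so its upper limit equals the point estimate, Day 57. The full set is (29, 85).

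| Percentile | SAP rule | Full set |
|---|---|---|
| 5th | 29 to 57 | 29 to 85 |
| 10th | 29 to 141 | 29 to 169 |
| 15th | 85 to 309 | 85 to not estimable |
| 20th | 113 to 309 | 113 to not estimable |

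The lower limits agree throughout.

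**How often.** Simulated arms of 115, 20% drop-out, visits exactly on schedule, 1,500 arms per row:

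| 52-week flare risk | Percentile | Finite but too early | Falsely finite |
|---|---|---|---|
| 10% | 5th | 61.1% | 38.6% |
| 10% | 10th | 2.8% | 96.5% |
| 20% | 5th | 98.9% | 0.1% |
| 20% | 10th | 85.7% | 13.9% |
| 20% | 15th | 32.9% | 66.9% |
| 20% | 20th | 3.4% | 94.8% |
| 30% | 20th | 68.1% | 31.1% |

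Where the correct limit was finite, the median shortfall was 28 days. With visits jittered by ±5 days the median was about 5 to 27 days. The SAP limit was never later than the correct one.

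**Coverage.** With 117 per arm, 18% drop-out, visits every 28 ± 4 days, and truth taken as the percentile of visit-recorded flare times, 10th-percentile coverage is about 93% under the SAP rule and about 96% for the full set. The 10th-percentile limit is falsely finite in about 52% of arms at 15% incidence and about 0.5% at 25%.

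**Critical value.** z(0.975) = 1.960. The printed 1.965 corresponds to 95.06%.

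**The case against.** No inference depends on these intervals. Significance for this endpoint rests on the stratified log-rank test within the hierarchy, and the effect size on the Cox hazard ratio. The percentile CIs are descriptive, within-arm, and computed the same way in every arm. All of this stands, and it bounds the importance of the point.

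The coverage loss is modest, and the full set errs the other way, at about 95.5 to 97.7% in the scenarios run. On coverage alone the two rules can be about equally far from 95%. That also stands. It does not excuse a finite limit where the data supply none.

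The steps sit under a heading of sample code, and step 4 speaks of values rather than times. But these are the only instructions for these CIs, and the natural reading is the flare times attached to the accepted values. Section 9.7 has a display convention for statistics that cannot be calculated. The rule does not trigger it, because it returns a number whenever any flare time lies in the band.

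Stronger readings that a reader might infer are not supported:

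- The upper limit is not always too early. The slightly wide 1.965 makes it coincide with the correct limit in up to about 2% of simulated arms, and with no flare time in the band nothing is returned.
- Taking a limit from an observed flare time is not itself the fault. A correct finite limit is also a flare time.
- The SAP does not call these percentiles the main summary of the endpoint or say why they were chosen. They appear beside the median, quartiles, flare counts and curves.

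**Conclusion.** The concern holds for the upper limit. As written, steps 2 and 4 do not produce the interval that the SAP's own formula defines. The limit is almost always one flare time early, about a month when visits are on schedule, and it is finite where it should be open. The false finiteness matters more, because follow-up ends at Week 52 and a low flare rate leaves many of these limits inestimable.

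The direction of the error follows from the rule and needs no assumption about the data. Its frequency depends strongly on flare incidence and drop-out, which the documents do not give: the 10th-percentile limit is falsely finite in about half of arms at 15% incidence but about 1% at 25%. The lower limit, point percentiles, log-rank test, Cox model and multiplicity procedure are unaffected. The 1.965 is a negligible slip. It works slightly against the main error, and because it sits in a formula read from PDF, an extraction error cannot be excluded.

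**What to change.** Replace step 4 with the log-log pointwise confidence limits of S(t):

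- Lower limit: the first flare time at which the lower pointwise limit is ≤ 1−p.
- Upper limit: the first flare time at which the upper pointwise limit is ≤ 1−p.
- Either one is reported as not estimable if no flare time qualifies.

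This also covers the case where no flare time falls in the band. Use quantile('NORMAL',.975), as the SAP's multiple-imputation code in 18.9.1 already does, in place of 1.965.

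The cost is a few lines of code, one sentence in 18.9.2, and a rerun of any table already produced with the old rule. Some intervals will become wider or open-ended.

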18.9.3 Other Secondary Endpoints

MMRM model: proc MIXED with SAS

For each continuous endpoint, the MMRM model will be implemented using the MIXED procedure.

A mixed model can be performed with SAS using the following code below. This sample code assumes the treatment group is assigned in the following order:

- 1 = Placebo
- 2 = Evobrutinib 25 mg QD
- 3 = Evobrutinib 75 mg QD
- 4 = Evobrutinib 50 mg BID

The interaction between treatment group and visit must be tested.

```
proc mixed data=<dataset>;
  where avisitn>1;
  class SubjectID Visit TreatmentGroup Region Race SLEDAI_2K_screening;
  model CHG = BASE TreatmentGroup Visit Region Race SLEDAI_2K_screening
  TreatmentGroup*Visit / ddfm=KR s;
  repeated Visit / sub=USUBJID type=UN ;
  lsmeans TreatmentGroup*Visit / pdiff /*e*/ cl;

  %*use estimates or results of PDIFF (DIFFS dataset) but inverse as pdiff
  gives trt=1 minus Trt=2/3/4;

  estimate 'Evobrutinib 25 mg QD - Placebo at W52' TreatmentGroup -1 1 0 0
    TreatmentGroup*Visit 0 0 0 0 0 0 0 0 0 0 0 0 0 0 0 0 0 0 0 0
  0 0 0 0 0 -1 1 0 0 / cl;
  estimate 'Evobrutinib 75 mg QD - Placebo at W52' TreatmentGroup -1 0 1 0
    TreatmentGroup*Visit 0 0 0 0 0 0 0 0 0 0 0 0 0 0 0 0 0 0 0 0
  0 0 0 0 0 -1 0 1 0 / cl;
  estimate 'Evobrutinib 50 mg BID - Placebo at W52' TreatmentGroup -1 0 0 1
    TreatmentGroup*Visit 0 0 0 0 0 0 0 0 0 0 0 0 0 0 0 0 0 0 0 0
  0 0 0 0 0 -1 0 0 1 / cl;  run ;

  ods output lsmeans=lsmeans diffs=diffs Tests3=Tests3;
```

where <TypeMatrix> represents the matrix of covariance (either type=CS or type=UN, see corresponding Section of the IAP for each endpoint). The 0 and 1 for visit and interaction treatment*visit must be adapted, depending on the number of assessments.

Logistic regression with repeated measures: GENMOD procedure from SAS

A logistic model with repeated measures can be implemented using the GENMOD procedure from SAS ® as follows:

```
ods listing close;
proc genmod data=<Dataset> descending;
class USUBJID Visit TreatmentGroup Region;
model AVAL = TreatmentGroup Visit Region TreatmentGroup*Visit / dist=bin
link=logit covb;
repeated subject=USUBJID / type=exch within=Visit;
estimate 'Evobrutinib 25 mg QD - Placebo at W52'
  TreatmentGroup -1 1 0 0
  TreatmentGroup*Visit 0 0 0 0 0 0 0 0 -1 1 0 0 / exp;
estimate 'Evobrutinib 75 mg QD - Placebo at W52'
  TreatmentGroup -1 0 1 0
  TreatmentGroup*Visit 0 0 0 0 0 0 0 0 -1 0 1 0 / exp;
estimate 'Evobrutinib 50 mg BID - Placebo at W52'
  TreatmentGroup -1 0 0 1
  TreatmentGroup*Visit 0 0 0 0 0 0 0 0 -1 0 0 1 / exp;

  lsmeans TreatmentGroup / ILINK CL;
  ods output Estimates=Estimates LSmeans=LSmeans Contrasts=Contrasts;
run;
quit;
ods listing;
```

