- A bar-chart figure of Mean score CFB at Week 52 presenting each SF-36 sub-domain score type (PF, RP, BP, GH, VT, SF, RE, MH) for each treatment will be provided.
- For PGIC, the number (proportion) of subject of subjects with any improvement (i.e., PGIC = 1, 2 or 3), no change (i.e., PGIC = 4) and any worsening (i.e., PGIC = 5, 6 or 7) will be summarized by visit and treatment group.

Probability of achieving %CFB value or higher:

For each SF-36 endpoint (domain scores, MCS, PCS), a figure will be provided describing the distribution of % CFB at Week 52, one curve per treatment group. The curve will display proportion of subjects having a value for % CFB > x at Week 52, where the range of x depends on the data. The same will be applied for FACIT-Fatigue total score and each domain score of LupusQoL.

Logistic regression:

Response on the SF-36, FACIT-Fatigue total score and PGIC will be further analyzed based on differences in proportion of responders, comparing each dose of evobrutinib to placebo.

Responder definitions will be based on minimal clinically important difference (MCID) criteria for improvement or deterioration from baseline as follows ([Strand 2005](#), [Lai 2011](#)):

- SF-36 – PCS & MCS:
 - Improvement is defined as an increase greater or equal to 2.5 compared to baseline
 - Deterioration is defined as a decrease greater or equal to 0.8 compared to baseline
- SF-36 – domain scores:
 - Improvement is defined as an increase greater or equal to 5.0 compared to baseline
 - Deterioration is defined as a decrease greater or equal to 2.5 compared to baseline
- FACIT-Fatigue Total Score:

- Improvement is defined as an increase greater or equal to 4.0 compared to baseline
- Deterioration is defined as a decrease greater or equal to 4.0 compared to baseline
- PGIC: improvement is defined as value = 1, 2 or 3

Logistic regression model for repeated measures will be applied, with adjustments for the randomization strata, baseline value and treatment as a factor. The estimated OR at Week 52, together with associated two-sided 95% CI of the estimated OR will be presented. For PGIC improvement, results will be presented at Week 12, 24, 40 and 52 visits. An example of SAS code is available in Appendix 18.9.

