18.9 SAS Sample Code

This Appendix details how the statistical methods will be implemented with SAS software application.

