			[140 ; 224)	Week 24 - Day 169 – LTE
			[224 ; 322)	Week 40 - Day 281 – LTE
			[322 ; 454)	Week 52 - Day 365 – LTE
			[454 ; 644)	Week 76 - Day 545 – LTE
[644 ; 751)	Week 104 - Day 745 – LTE			

* Assessments performed more than 14 days after last exposure date will not be included as well as assessments collected during safety follow-up visit.

Table 60: Time Windows for PGIC

Analysis	Treatment groups	Period covered	Interval (days) [Date of assessment – Date of first dose + 1]	Analysis Visit
• PA	
 • Placebo • Evobrutinib 25 mg QD • Evobrutinib 75 mg QD • Evobrutinib 50 mg BID 	52-week treatment period	[1 ; 42)	Week 4 – Day 29
			[42 ; 70)	Week 8 – Day 57
			[70 ; 98)	Week 12 – Day 85
			[98 ; 140)	Week 16 – Day 113
			[140 ; 196)	Week 24 – Day 169
			[196 ; 252)	Week 32 – Day 225
			[252 ; 322)	Week 40 – Day 281
≥ 322*	Week 52 – Day 365			
• LTE analysis	
 • Placebo/Evobrutinib 50 mg BID • Evobrutinib 25 mg QD/Evobrutinib 50 mg BID • Evobrutinib 75 mg QD/Evobrutinib 50 mg BID • Evobrutinib 50 mg BID/Evobrutinib 50 mg BID 	52-week treatment period	NA	NA
		LTE period	1	Day 1 – LTE
			[2 ; 266)	Week 24 - Day 169 – LTE
			[266 ; 554)	Week 52 - Day 365 – LTE
		[554 ; 751)	Week 104 - Day 745 – LTE	

* Assessments performed more than 14 days after last exposure date will not be included as well as assessments collected during safety follow-up visit.

Table 61: Time Windows for ECG

Analysis	Treatment groups	Period covered	Interval (days) [Date of assessment – Date of first dose + 1]	Analysis Visit
• PA	
 • Placebo • Evobrutinib 25 mg QD • Evobrutinib 75 mg QD • Evobrutinib 50 mg BID 	52-week treatment period	1	Day 1
			[2 ; 126)	Week 12 – Day 85
			[126 ; 224)	Week 24 – Day 169
			[224 ; 322)	Week 40 – Day 281
			≥ 322*	Week 52 – Day 365
• LTE analysis	
 • Placebo/Evobrutinib 50 mg BID • Evobrutinib 25 mg QD/Evobrutinib 50 mg BID • Evobrutinib 75 mg QD/Evobrutinib 50 mg BID • Evobrutinib 50 mg BID/Evobrutinib 50 mg BID 	52-week treatment period	NA	NA
		LTE period	1	Day 1 – LTE
			[2 ; 126)	Week 12 - Day 85 – LTE
			[126 ; 266)	Week 24 - Day 169 – LTE
			[266 ; 454)	Week 52 - Day 365 – LTE
			[454 ; 644)	Week 76 - Day 545 – LTE
[644 ; 751)	Week 104 - Day 745 – LTE			

* Assessments performed more than 14 days after last exposure date will not be included as well as assessments collected during safety follow-up visit.

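### The sample code for the repeated-measures logistic responder analyses adjusts for region only, while SAP Section 14.3.4 requires all randomization strata and the baseline value

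*SAP*

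**What the plan says.** Section 14.3.4 (HRQoL) sets out which endpoints get a responder analysis: "Response on the SF-36, FACIT-Fatigue total score and PGIC will be further analyzed based on differences in proportion of responders". For the model it says: "Logistic regression model for repeated measures will be applied, with adjustments for the randomization strata, baseline value and treatment as a factor". It then refers to Appendix 18.9 for example code.

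The strata are named elsewhere in the SAP. Section 14.2.2.2, for instance, lists the "stratification variables used in the randomization (race, screening SLEDAI-2K total score and region) as covariates", and Section 14.1.2.1 names the same three factors.

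The code for this model is in Section 18.9.3. Its CLASS statement is "class USUBJID Visit TreatmentGroup Region" and its MODEL statement is "model AVAL = TreatmentGroup Visit Region TreatmentGroup*Visit / dist=bin".

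Just above it, the mixed-model code for the continuous quality-of-life scores starts with "model CHG = BASE TreatmentGroup Visit Region Race SLEDAI_2K_screening".

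Section 18.9 describes the status of the code in these words: "This Appendix details how the statistical methods will be implemented with SAS software application".

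**The concern.** Text and code specify different models for the same analysis. The code cannot simply be ignored in favour of the text. It is the only place that gives the visit effect, the treatment-by-visit interaction, the exchangeable working correlation and the choice of GENMOD. A programmer has to use it, and nothing in Section 18.9.3 warns that covariates are missing.

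For SF-36 and FACIT-Fatigue, response is a change from baseline past a threshold (2.5 points up for PCS and MCS, 4.0 for FACIT-Fatigue). A subject's starting score then predicts response through regression to the mean, which is a statistical argument and not something the SAP states. Leaving baseline out changes what the odds ratio measures, because conditional and marginal odds ratios differ, and it costs power. The same scores would also be baseline-adjusted as continuous outcomes and unadjusted as responder outcomes.

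**Working it through.** **1. Terms required against terms coded.**

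| Term | Text, 14.3.4 | GENMOD code, 18.9.3 | Mixed-model code, 18.9.3 |
|---|---|---|---|
| Treatment | yes | yes | yes |
| Region | yes (stratum) | yes | yes |
| Race | yes (stratum) | no | yes |
| Screening SLEDAI-2K | yes (stratum) | no | yes |
| Baseline value | yes | no | yes |
| Visit, treatment by visit | not mentioned | yes | yes |

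Three of the four adjustment terms in the text are absent from the code. This is not a house shorthand: the primary logistic code (18.9.1) and the log-rank, Cox and negative binomial code (18.9.2) all list region, race and screening SLEDAI-2K.

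**2. PGIC.** Section 18.6 describes PGIC as a rating of change since treatment began. In Section 18.11, "Table 60: Time Windows for PGIC" has no Day 1 row; its first window is Week 4. No baseline value exists, so the text cannot be followed literally for PGIC. Only race and screening SLEDAI-2K are missing from the PGIC code.

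**3. Contrasts.** Each ESTIMATE row has 12 interaction coefficients, and 12 / 4 arms = 3 visits, with the contrast on the third. Table 57 has eight post-baseline visits for SF-36 and FACIT-Fatigue (Weeks 4, 8, 12, 16, 24, 32, 40 and 52), so a Week 52 contrast needs 8 × 4 = 32 positions. PGIC is to be reported at four visits (Weeks 12, 24, 40 and 52), also more than three. Unedited, the rows do not give the Week 52 contrast.

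**4. Size of the loss for a change-based responder.** The SAP states no figure here, so this is an illustration.

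- From the SAP: 108 per arm (8.2.1); SD 10, the general-population norm for PCS and MCS (18.3); responder = change of at least 2.5; two-sided 0.05 (14.3).
- Assumed: baseline-to-Week-52 correlation ρ of 0.3, 0.5 or 0.7; a 4-point treatment effect; a mean placebo change of 2.5, which makes the placebo response 50%.
- Method: 1500 simulated two-arm data sets per setting, ordinary logistic regression at one visit, with and without baseline. Race and screening SLEDAI-2K were not simulated.

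Hand check of the unadjusted odds ratio: SD of change = 10·√(2(1−ρ)), and response on active = Φ(4 / SD of change).

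- ρ = 0.3: SD 11.83, Φ(0.338) = 0.632, odds ratio 0.632/0.368 = 1.72
- ρ = 0.5: SD 10.00, Φ(0.400) = 0.655, odds ratio 0.655/0.345 = 1.90
- ρ = 0.7: SD 7.75, Φ(0.516) = 0.697, odds ratio 0.697/0.303 = 2.30

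These agree with the simulated 1.72, 1.89 and 2.32.

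| ρ | OR without baseline | OR with baseline | OR lower by | Power without | Power with | Loss (points) |
|---|---|---|---|---|---|---|
| 0.3 | 1.72 | 2.03 | 1 − 1.72/2.03 = 15% | 47.7% | 60.1% | 12.4 |
| 0.5 | 1.89 | 2.15 | 1 − 1.89/2.15 = 12% | 61.3% | 69.9% | 8.6 |
| 0.7 | 2.32 | 2.55 | 1 − 2.32/2.55 = 9% | 84.5% | 87.8% | 3.3 |

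The absolute correlation between baseline and change ran from 0.37 to 0.59, which is why baseline carries this weight.

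With no treatment effect, rejection was 4.9% to 5.1% without baseline and 4.7% to 5.7% with it.

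**The case against.** The strongest reply is that the specification is Section 14.3.4, and it is right. Appendix 18.9 is titled as sample code, Section 14.3.4 calls it an example, and the block is introduced in permissive terms. The contrast rows show that it is a template that needs editing, and the mixed-model section says its own coefficients must be adapted to the number of assessments. This stands in part. A reader might infer that the trial's responder odds ratios are in fact unadjusted. The SAP does not show that; it follows only if the code was run as written. The conflict remains, because Section 18.9 presents the appendix as the way the methods will be carried out, and the adaptation note concerns coefficients, not covariates.

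Two other objections stand fully. First, the SAP gives no responder rates, effect size or power target for these endpoints, and the analysis is repeated-measures, so single-visit figures are only illustrative. Second, Section 14.3 makes these p-values nominal, the endpoints are outside the hierarchy in Section 14.1.2.4, and the sample mixed-model code for the same SF-36 and FACIT-Fatigue scores has baseline and all strata.

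A reader might also infer that PGIC loses its main predictor, or that false positives increase. Neither holds: PGIC has no baseline value, and the simulated rejection rate under the null is about 5% either way.

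**Conclusion.** The contradiction between Sections 14.3.4 and 18.9.3 is real. The sample code omits race and screening SLEDAI-2K for all three instruments, and baseline for SF-36 and FACIT-Fatigue. Run as written, it would estimate a marginal odds ratio about 9% to 15% smaller than the baseline-adjusted one and lose about 3 to 12 power points. Both ranges depend on the assumed correlation of 0.3 to 0.7, the 4-point effect and the single-visit model. They cover baseline only, not the two missing strata.

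The text has a smaller fault of its own: it asks for a baseline value that PGIC does not have.

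Severity is minor. The issue affects the estimate, its efficiency and the reproducibility of nominal secondary analyses, not the study's type I error or its primary conclusions. Because this SAP version was written after the primary analysis had been reviewed (Sections 6.3 and 6.4), lost power can no longer be prevented prospectively. What can still be settled is which model produced the results.

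**What to change.** - In the GENMOD code of Section 18.9.3, add Race and SLEDAI_2K_screening to both CLASS and MODEL.
- Add BASE to MODEL for SF-36 and FACIT-Fatigue.
- State in Section 14.3.4 that the PGIC model has no baseline term.
- Adapt the interaction coefficients in the ESTIMATE rows to the visits actually in each model, so that they give Week 52, and also Weeks 12, 24 and 40 for PGIC.
- Record in the study report which model was run for the primary analysis. If it was the sample code as written, rerun the stated model and say so.

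The cost is a few model terms, one clause of text and longer contrast rows. All the variables already appear in the neighbouring mixed-model code. A rerun is needed only if the incomplete model was used.
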